5.1.3 Missing value imputation of primary endpoint

Missing value imputation for the primary endpoint, i.e. the number of RP attacks in a week prior to the week 4 visit (i.e for patients missing a week 4 diary due to early discontinuation or a lost diary) will be done as follows:

Placebo multiple imputation assumes that the statistical behaviour of drug- and placebo-treated patients after discontinuing study medication becomes that of placebo-treated patients. Multiple imputations (MIs) are used to replace missing change from baseline at week 4 outcomes for drug- and placebo-treated patients who discontinued utilizing multiple draws from the posterior predictive distribution estimated from the placebo arm, based on the ANCOVA

Statistical Analysis Plan	Version 2.0		Page 18 of 19
Sponsor	Gesynta Pharma AB	Protocol No	GS-2001

(Analysis of Covariance) model including the stratification factor (vasodilatory treatment i.e., Ca-blockers, PDE-5 inhibitors, or no background vasodilatory treatment) and treatment as fixed factors and baseline levels as a covariate in the model.

The final inference on treatment difference is conducted from the multiple datasets using Rubin's combining rules as implement in SAS PROC MI ANALYSE. Thus, in the effectiveness context, pMI assumes no pharmacological benefit of the drug after dropout. In the efficacy context, pMI is a specific form of a missing-not-at-random (MNAR) analysis expected to yield a conservative estimate of efficacy.

This process will be performed for both the FAS and PP set.

5.1.4 Descriptive statistics

Descriptive statistics will be presented for the number of RP attacks by visit and mean change between visit 4 and baseline, using observed data only.

The analysis of the primary endpoint will be performed using analysis of covariance, AN-COVA), including the stratification factor (vasodilatory treatment i.e., Ca-blockers, PDE-5 inhibitors, or no background vasodilatory treatment) and treatment as fixed factors and baseline levels as a covariate in the model.

5.1.5 Statistical inference on Mean change in number of RP attacks

The null hypothesis is that there is no difference between treatments.

Mean change in the number of RP attacks from baseline to week 4 will be tested using the following:

$$\begin{aligned}\mu_1 &= \text{mean change in active treatment group} \\ \mu_2 &= \text{mean change in placebo group}\end{aligned}$$

The following hypothesis is set for μ_1 and μ_2 :

$$\begin{aligned}H_0 &: \mu_1 = \mu_2 \\ H_a &: \mu_1 \neq \mu_2\end{aligned}$$

The primary objective will be met if there is a p-value <0.05 with a numerical superior efficacy of the active group versus placebo with regard to the primary endpoint, i.e. the mean change (reduction) in RP attacks that is greater in the active group.

Results for the outcome of the primary endpoint will be presented for the least square means estimates and accompanying 95% CIs.

Analysis will be done on the FAS and PP population. The primary analysis population is the FAS.

5.1.6 Robustness

Residuals will be used to assess the adequacy of the ANCOVA model and to detect outliers and influential points.

Statistical Analysis Plan	Version 2.0		Page 19 of 20
Sponsor	Gesynta Pharma AB	Protocol No	GS-2001

As a exploratory analysis, analysis will be done on the observed cases only, i.e., with no imputation

5.2 Key Secondary endpoints

If the primary efficacy endpoint achieves superiority, $p < 0.05$, formal statistical testing of the secondary efficacy endpoints will be performed using a closed testing procedure:

The overall type I family-wise error rate for testing the primary and the key secondary efficacy endpoints will be controlled at the 0.05 significance level using the following 2-family serial gatekeeping multiple comparisons procedure (MCP). Following this MCP, progression to the next family will only occur if the null hypothesis with-in the current family is rejected at a family-specific overall significance level. If the null hypothesis within a family is not rejected, the statistical tests corresponding to all subsequent families will be considered not statistically significant. All hypothesis tests will be 2-sided.

1. The first family will include the primary endpoint: The p-value for the null hypotheses must be less than 0.05 to be considered to have met the primary efficacy objective. If the primary efficacy null hypotheses is not rejected (i.e., $p\text{-value} > 0.05$), all subsequent statistical tests, i.e. on key secondary and will not be considered statistically significant.

2. The second family will include the key secondary endpoints (see below) and they will be tested using an over-all type I error rate of 0.05 by means of a hierarchical procedure in order to control for multiplicity within this family. The hierarchical order to test the key secondary variables will be the following:

Due to the closed testing procedure, no correction for multiplicity is necessary. If superiority cannot be shown, the secondary endpoints will be presented using descriptive statistics, per treatment, and nominal p-values.

The secondary endpoints will be analysed using the following hierarchical test order:

- 1) Pain
- 2) Raynaud's Condition Score
- 3) Duration of RP attacks

5.2.1 Mean change from baseline to week 4 in pain experienced during RP attacks

For each RP attack the pain experienced during the RP attack is scored rating from 0 (No pain) to 10 (Worst imaginable pain).

For the baseline week and for week 4 the individual mean pain scores of the RP attacks in the 7 most recent days before a Visit (Visit 2 and Visit 4), will be derived by calculating the sum of individual pain scores of each RP attack in the 7 most recent days before the Visit divided by the number of RP attacks in the same period.

Change in mean daily pain will be calculated as the mean of the individual mean pain score at Visit 4 minus the individual mean pain score at Visit 2.

If there are no attacks in a week, the pain score has no eligible values and in the calculations, it will be set to missing.

Statistical Analysis Plan	Version 2.0		Page 20 of 21
Sponsor	Gesynta Pharma AB	Protocol No	GS-2001

The analysis of the mean daily pain experienced during RP attacks endpoint will be similar to the analysis of the primary endpoint

5.2.2 Mean change from baseline to week 4 in the Raynaud’s Condition Score (RCS)

Each day, at bedtime the RCS, rating how much difficulty the subject had with their Raynaud’s that day on a scale from 0 (No difficulty) to 10 (Extreme difficulty). Blinded diary data review showed that patients could enter more than 1 RCS score on a day. Daily RCS scores are identified in the diary database through the window date. If more than 1 RCS score was entered with the same window date, the last entry (identified either by the event time or by the visit, was used as the daily RCS score for that date. The other entry on that date is kept in the raw data-sets, but not used in the derivation of the daily RCS score.

Derivation of mean RCS score in 7 days preceding a visit

The mean RCS score in the 7 days preceding a visit is defined as the mean of the non-missing RCS scores of 7 most recent days prior to the visit.

Change in mean RCS score will be calculated as the mean of the individual mean RCS score at visit 4 minus the mean of the individual mean RCS score at baseline.

The analysis of the Raynaud’s Condition Score endpoint will be similar to the analysis of the primary endpoint.

5.2.3 Mean change from baseline to week 4 in the cumulative and mean duration of RP attacks

For each RP attack the duration can be derived from the start and stop time points.

The cumulative RP attack duration is defined as follows:

- 1) Determine the sum of confirmed RP attacks duration on the 7 most recent days with confirmed RP attack information prior to a visit.
- 2) Determine the mean RP attack duration by dividing the sum of confirmed RP attack duration by the number of confirmed RP attacks.
- 3) Multiply the mean RP attack duration of confirmed RP attacks with the number of RP attacks (including imputations) as derived in 5.1.1 to come to the cumulative RP attack duration.

Blinded Diary review showed that for RP attack duration, some patients entered a stop date/time of an RP attack that was before the start date/time of the RP attack. For these entries the following rules will be applied:

- For the overlapping events – the latest entered event of the overlapping ones (using SEQ no. in the database) will be used. The other entry will not be used in any attack reporting (RPA, Pain, duration i.e. not be counted at all). The information will be kept in the raw data-sets.
- If stop time was before start time – duration will be set to missing, but attacks will as be counted as confirmed attacks in RPA and Pain derivations

Statistical Analysis Plan	Version 2.0		Page 21 of 22
Sponsor	Gesyntha Pharma AB	Protocol No	GS-2001

- If recall period > 1 day this will be a minor protocol deviation, recalled data will not be excluded from the analysis.

Blinded review of the derived cumulative and mean RP attack duration as derived of the 7 most recent days prior to a visit showed that the derived values have a skewed distribution. For that reason, the evaluation of cumulative RP attack duration and mean RP attack duration will be done on natural log scale.

For each patient change in log-transformed cumulated RP attack duration and log-transformed mean RP attack duration will be derived as follows:

- Change = LN(cumulative RP attack duration prior to week 4 visit) – LN(cumulative RP attack duration prior to baseline visit)
- Change = LN(mean RP attack duration prior to week 4 visit) - LN(mean RP attack duration prior to baseline visit)

The analysis of the mean change in LN(cumulative duration of RP attacks) and mean change in LN (mean RP attack duration) will be similar to the analysis of the primary endpoint.

Descriptive statistics will be provided for the cumulative RP durations and mean RP attack durations on both the absolute and the log-transformed scales. After summarizing the log-transformed values, the back-transformed values of the descriptive statistics of the log-transformed values and of the descriptives of the changes on log-scale will be created for these parameters at baseline visit and week 4 visit.

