1 STUDY INFORMATION

1.1 Primary objective

Objectives	Endpoints

Primary: To determine the safety and efficacy of GS-248 versus placebo on RP in subjects with SSc.
	
EFFICACY
 
Primary Efficacy: Mean change from baseline to week 4 in the number of Raynaud’s Phenomenon attacks per week.
 
Key secondary efficacy:
 
 • Mean change from baseline to week 4 in the Raynaud’s Condition Score (RCS). • Mean change from baseline to week 4 in the cumulative duration of Raynaud’s Phenomenon attacks. • Mean change from baseline to week 4 in pain experienced during RP attacks. 
Exploratory efficacy:
 
 • Patient Global Impression of Change at week 4. • Physician Global Impression of Change at week 4. • Mean change in ASRAP Questionnaire score from baseline to week 4. 
SAFETY
 
Safety Endpoints:
 
 • Incidence of Adverse events. • Incidence of Serious Adverse Events. • Clinical laboratory and vital signs.

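### Step 3 of the key secondary hierarchy, duration of RP attacks, covers two tested variables with no order or decision rule, while the protocol and SAP 1.1 name cumulative duration only

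*SAP*

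**What the plan says.** SAP 5.2 sets up a two-family serial gatekeeping procedure at an overall two-sided 0.05. The primary endpoint comes first, followed by the key secondary endpoints in the order pain, RCS, duration. It adds: "Due to the closed testing procedure, no correction for multiplicity is necessary". The third step is written only as "3) Duration of RP attacks".

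The section that defines this step, SAP 5.2.3, is headed "Mean change from baseline to week 4 in the cumulative and mean duration of RP attacks", and SAP Appendix 2 repeats that line under the key secondary endpoints. Section 5.2.3 defines a log-scale change for each variable and gives both the same inferential treatment: "The analysis of the mean change in LN(cumulative duration of RP attacks) and mean change in LN (mean RP attack duration) will be similar" to that of the primary endpoint. It also fixes the link between them. Cumulative duration is obtained by this rule: "Multiply the mean RP attack duration of confirmed RP attacks with the number of RP attacks (including imputations) as derived in 5.1.1".

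Elsewhere only one duration variable appears. SAP 1.1 lists "Mean change from baseline to week 4 in the cumulative duration of" RP attacks. Protocol Table 2.1, 6.1.2, 8.5.2 and Appendix 8 also name cumulative duration alone. SAP 2.2 lists changes to the FAS and PKAS definitions and does not mention an added key secondary variable. Protocol 8.5.2 leaves the detail of the multiplicity procedure to the SAP.

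**The concern.** A fixed test order controls the family-wise error without correction only if each step holds one hypothesis, or if a step with several has a rule that keeps its own error at 0.05. Step 3 has a single label, two variables behind it and no such rule. Taken at face value, SAP 5.2.3 and Appendix 2 put two uncorrected 0.05 tests there.

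The study report could then present two duration p-values as confirmatory where the protocol planned one. Alternatively, the choice between them could be made once the results are known. The two variables are not interchangeable: a drug that makes attacks rarer but no shorter lowers cumulative duration and leaves mean duration unchanged.

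**Working it through.** **1. The stated 0.05.** With one hypothesis per step, each tested at 0.05, a family-wise error requires rejection of the first true null in the sequence. That has probability at most 0.05. The SAP's figure is reproduced for a step 3 with one variable.

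**2. How the two variables are linked.** SAP 5.2.3 makes cumulative duration = mean duration × weekly number of attacks. On the log scale, change in LN(cumulative) = change in LN(mean) + change in LN(count), so the treatment effects satisfy δ_cum = δ_mean + δ_count. Both duration nulls are true only if δ_mean = 0 and δ_count = 0. If exactly one is true, only that test can err, and the step-3 error is at most 5% under any rule.

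**3. Step-3 error by reading, both nulls true and earlier steps passed.** Let Z1 and Z2 be the two test statistics, bivariate normal with correlation ρ. The documents give no ρ, so a range is assumed; 0.71 is 1/√2, the value when LN(mean) and LN(count) are independent with equal variance.

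- Cumulative duration alone, or a fixed order: 0.05.
- Both must be significant: P(|Z1| > 1.96 and |Z2| > 1.96).
- Either suffices: 1 − P(|Z1| < 1.96, |Z2| < 1.96). At ρ = 0 this is 1 − 0.95² = 0.0975.
- False claim of benefit, either suffices: 1 − P(Z1 < 1.96, Z2 < 1.96). This direction is relevant because the primary claim in SAP 5.1.5 needs "a p-value <0.05 with a numerical superior efficacy of the active group versus placebo", and the duration analysis follows the primary one. The reference value is 0.025.

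| Assumed ρ | Both must win | Either wins, two-sided | Either wins, false benefit |
|---|---|---|---|
| 0 | 0.0025 | 0.0975 | 0.0494 |
| 0.5 | 0.0093 | 0.0907 | 0.0454 |
| 0.71 | 0.017 | 0.083 | 0.042 |
| 0.9 | 0.030 | 0.0704 | 0.0352 |

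Only the either-wins reading exceeds 5% two-sided. It returns to 5% only at ρ = 1.

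**4. Dependence on the earlier steps.** The table treats the earlier steps as independent of the duration tests. As a sensitivity check, assume that the primary statistic has correlation 0.8 with the log-count statistic, that the primary gate has 80% power, and that the variance shares are equal. At ρ = 0.71 the conditional two-sided rate then moves from 0.083 to 0.074, and the benefit rate from 0.042 to 0.046.

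**5. Conditional and unconditional rates.** The table is conditional on reaching step 3. Under independence, the unconditional rate is the tabled rate times the chance of passing primary, pain and RCS. It exceeds 5% if that joint chance is above 0.05/0.0831 = 60% at ρ = 0.71, or above 0.05/0.0704 = 71% at ρ = 0.9. In the sensitivity case, with the primary gate alone, it is 0.074 × 0.80 = 0.059. The documents give no power for pain or RCS.

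**6. Whether the choice of variable changes the answer.** This is an illustration under assumed inputs and not an error rate. Take LN(mean) and LN(count) as independent, give LN(mean) a share w of the variance of LN(cumulative), and shift one component by 2.80 standard errors (80% power). The earlier steps are ignored. The two variables give different two-sided verdicts in this fraction of trials:

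| w | Drug lowers count only | Drug shortens attacks only |
|---|---|---|
| 0.2 | 69% | 59% |
| 0.5 | 51% | 33% |
| 0.8 | 24% | 14% |

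**The case against.** The strongest reply is that the documents nearly answer the question. SAP 1.1 lists three key secondary endpoints and SAP 5.2 lists three steps. They match one to one if step 3 is cumulative duration, and the protocol agrees throughout. Within 5.2.3, mean duration first appears as an intermediate quantity in deriving cumulative duration. Being analysed similarly to the primary endpoint may mean no more than using the same ANCOVA model. No passage says that either variable suffices. This makes cumulative duration the best-supported reading. It does not settle the matter, because 5.2.3 and Appendix 2 give mean duration the same key secondary status and its own comparison, and the SAP is where the protocol says the procedure will be detailed.

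The error figures can also be challenged. They are conditional on three earlier successes, and they need a real effect on weekly attack count with none on log count, which is close to degenerate. That is correct, and the figures should be read as a worst case. A claim of family-wise control has to cover the worst case, however, and as the earlier gates approach certain passage the rate does exceed 5%.

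Finally, SAP 2.2 lists only deviations considered important, so its silence on mean duration is weaker evidence than the direct mismatch between sections. That point also stands.

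**Conclusion.** The concern holds. The SAP adds a second key secondary duration variable, contrary to the protocol and to its own section 1.1, and gives no rule for a step that now contains two tests. The claimed 0.05 control is therefore not guaranteed as written, although it holds under three of the four possible readings, including the best-supported one. Inflation is not certain. It arises only if success on either variable counts, both duration nulls are true and step 3 is reached, and its size depends on an assumed correlation.

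The more practical risk is an undeclared choice between two variables that can disagree. The consequence is limited to the last key secondary step. It should be corrected, but it does not threaten the main conclusion of the trial.

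**What to change.** In SAP 5.2, replace the step-3 label with the between-group comparison of change in LN(cumulative RP attack duration), the protocol endpoint, as the sole hypothesis at that step. Align SAP 5.2.3 and Appendix 2 by moving mean attack duration to the exploratory endpoints with a nominal p-value. If the sponsor wants a confirmatory claim on mean duration, make it an ordered step 4, tested at 0.05 only after step 3 succeeds, and record the addition in SAP 2.2.

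The cost is a few lines of wording in those sections before unblinding. No new data and no additional analyses are needed.

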#### 6.1.2 Key Secondary Efficacy Endpoints

- The mean change in RCS from baseline (from the 7 most recent days prior to Visit 2) to week 4 (from the 7 most recent days prior to Visit 4) will be collected prior to each visit using data entered by subjects in the eDiary.
- The mean change in cumulative duration of RP attacks from baseline (from the 7 most recent days prior to Visit 2) to week 4 (from the 7 most recent days prior to Visit 4) will be collected prior to each visit using data entered by subjects in the eDiary.
- Data for numeric rating scale (NRS) pain will be assessed using eDiaries, and the mean change in pain experienced during RP attacks from baseline (from the 7 most recent days prior to Visit 2) to week 4 (from the 7 most recent days prior to Visit 4) will be collected prior to each visit using data entered by subjects in the eDiary.

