5.1.1 Diary: Number of RP attacks

RP attacks in the daily diary

RP attacks are captured in the diary. For each RP attack the date, start time, stop time and the experienced pain (scale of 0 (No pain) to 10 (worst imaginable pain)) is captured. If an RP attack continues into the next day, the RP attack is counted on the date the attack started.

In addition to the daily entry of RP attacks in the diary, the diary is organized in such a way that patients are asked, through the previous attack details form, whether they had any RP attacks on the previous day:

- Did you have any attacks yesterday (CEPERF=Yes/No)
- Did you record them all in the diary (CECONF=Yes/No)

The replies to these questions are used for the interpretation of the RP attacks recorded in the diary in the following way:

Statistical Analysis Plan	Version 2.0		Page 17 of 18
Sponsor	Gesynta Pharma AB	Protocol No	GS-2001

If the patient answers (CEPERF=No) or the patient answers (CEPERF=Yes and CECONF=Yes), it is assumed that RP attacks on the previous day are recorded as instructed.

If the patient confirms both questions (CEPERF=Yes and CECONF=Yes), it is assumed that RP attacks on the previous day are recorded as instructed.

If the patient answers CEPERF=Yes and CECONF=No, and any RP attacks are recorded on the previous day, it is assumed that RP attacks on the previous day are recorded as instructed.

If the patient answers CEPERF=Yes and CECONF=No, and no RP attacks are recorded on the previous day, it is assumed the RP attacks on the previous day are confirmed missing.

Missing value imputation to come to number of RP attacks in the 7 days preceding a visit

For each day, starting during the baseline diary week, the number of recorded RP attacks as defined above and the number of days with confirmed RP attack information, are counted.

For the baseline week and for week 4 the number of daily attacks in the 7 most recent days before a visit (Day 1 and Day 28 (-2/+1)), will be derived by calculating the mean number of daily RP attacks on the days with RP attack information in the 7 most recent days and subsequently imputing this mean on the days with confirmed missing RP attack information in the 7 most recent days in the following way:

- 1) Summing the number of confirmed RP attacks in the 7 most recent days before a visit (total number of confirmed RP attacks)

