- 2) Dividing this sum by the number of days with confirmed RP attack information in the 7 most recent days before a visit (=mean daily number of confirmed RP attacks)
- 3) Multiplying this mean number of daily attacks with 7.

This derivation results in the number of RP attacks in a week.

5.1.2 Derivation of the mean change from baseline to week 4 number of RP attacks

The primary endpoint for this study is the mean change from baseline to week 4 in the number of Raynaud's Phenomenon attacks per week as derived in 5.1.1 i.e., number of RP attacks in week 4 minus the number of RP attacks during the baseline week, where a decrease change in the number of RP attacks at week 4 compared to baseline indicates an improvement compared to baseline

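### SAP 5.2.3 sums attack durations over the seven most recent informative days while SAP 5.1.1 counts attacks over seven calendar days, so cumulative duration can combine different days

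*SAP*

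**What the plan says.** SAP 5.2.3 builds the cumulative duration as follows.

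- Step 1: "Determine the sum of confirmed RP attacks duration on the 7 most recent days with confirmed RP attack information prior to a visit".
- Step 2: "Determine the mean RP attack duration by dividing the sum of confirmed RP attack duration by the number of confirmed RP attacks". No window is given and no other section is cited.
- Step 3: multiply that mean "with the number of RP attacks (including imputations) as derived in 5.1.1 to come to the cumulative RP attack duration".

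The count that step 3 uses comes from SAP 5.1.1, which works within a fixed week: "Summing the number of confirmed RP attacks in the 7 most recent days before a visit (total number of confirmed RP attacks"), then "Dividing this sum by the number of days with confirmed RP attack information in the 7 most recent days before a visit", then "Multiplying this mean number of daily attacks with 7". Informative days are a subset of that week, so the seven days must be calendar days.

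Other places also put duration in the calendar week. Later in SAP 5.2.3, the blinded review describes the "cumulative and mean RP attack duration as derived of the 7 most recent days prior to a visit". Protocol 6.1.2 has "The mean change in cumulative duration of RP attacks from baseline (from the 7 most recent days prior to Visit 2") and the matching window for Visit 4. Protocol 8.5.1, applied to the key secondary endpoints by 8.5.2, and Appendix 8 use the same seven days. (Appendix 8 prints Visit 4 for both visits in the duration row, but the length of the window is clear.)

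SAP 5.2.3 also sets the duration to missing when an attack's stop precedes its start, while keeping that attack in the attack count and the pain score. Cumulative and mean duration are both analysed as changes in the natural log.

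**The concern.** The wording of step 1 differs from that of 5.1.1. One takes the last seven days that carry information, however far back they lie. The other takes the last seven days and uses those that carry information. The two agree only when no day in the week is uninformative.

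With an uninformative day, the mean duration in step 2 draws on at least one day outside the week, and step 3 multiplies it by a count from inside the week. At Visit 4 the added days precede week 4, so an earlier stage of treatment enters an endpoint defined at week 4. In addition, because step 2 names no window, two programmers could use different divisors and obtain different values for the same subject. At stake are the values of a key secondary endpoint, and of the mean duration analysed beside it, for subjects with incomplete diaries.

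**Working it through.** The plan gives no figure for this endpoint to reproduce; its sample size calculation concerns the primary endpoint and does not enter here.

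**Which days are used.** Visit 4 is nominally Day 28, so the calendar week is Days 21 to 27. With two uninformative days in it, and complete earlier days, step 1 adds Days 20 and 19. Before Visit 2 on Day 1 the week is Days -7 to -1, and step 1 adds Days -8 and -9.

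**Inputs.** Let k be the number of informative days in the calendar week, with earlier days complete. The randomisation criteria in protocol 4.1 require diary records on at least 5 of 7 days at baseline. That rule concerns submitted records, which is not identical to the confirmed attack information of SAP 5.1.1, so k = 5 is only a guide. I found no minimum for week 4. For illustration I assume 2 attacks a day of 20 minutes each.

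**Aligned value, same days throughout (k = 5).** Sum 5 × 2 × 20 = 200 minutes; attacks 5 × 2 = 10; mean 200/10 = 20; weekly count 10/5 × 7 = 14; cumulative 20 × 14 = 280 minutes. The result is 280 for any k from 1 to 7.

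**Step 1 as written.** The sum is always 7 × 2 × 20 = 280 minutes. The divisor depends on how step 2 is read:

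| k | Divisor = the attacks summed in step 1 | Divisor = the 5.1.1 count (2k) | Second reading / aligned = 7/k | ln(7/k) |
|---|---|---|---|---|
| 7 | 280/14 × 14 = 280 | 280/14 × 14 = 280 | 1.00 | 0 |
| 6 | 280/14 × 14 = 280 | 280/12 × 14 = 327 | 1.17 | 0.154 |
| 5 | 280/14 × 14 = 280 | 280/10 × 14 = 392 | 1.40 | 0.336 |
| 4 | 280/14 × 14 = 280 | 280/8 × 14 = 490 | 1.75 | 0.560 |

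**When duration is not stable (k = 5).** Suppose the two added days had attacks of 40 minutes. The sum is 5 × 2 × 20 + 2 × 2 × 40 = 360. On the first reading the cumulative value is 360/14 × 14 = 360, which is 1.29 times the aligned 280 (log +0.251). On the second it is 360/10 × 14 = 504, or 1.80 times (log +0.588). If the added days had shorter attacks, the first reading would move the other way.

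**Effect on the change score.** On the second reading at a constant rate, the shift in a subject's log change is ln(7/k at week 4) − ln(7/k at baseline) = ln(k at baseline / k at week 4). It is zero when completeness is equal at both visits. Going from 7 to 5 gives +0.336, which understates that subject's improvement. Across arms, only a difference between the arms' average shifts biases the comparison.

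**Attacks without a usable duration.** Take the aligned case of 10 attacks and let one have its stop before its start. The sum is 9 × 20 = 180. Dividing by 10 gives a mean of 18 and a cumulative value of 18 × 14 = 252; dividing by the 9 attacks with a duration gives 20 and 280. Aligning the days alone would leave this open.

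**The case against.** A reader might infer that the SAP inflates duration by 7/k for every incomplete diary. The documents do not establish that. Step 2 neither names a window nor cites 5.1.1, whereas step 3 cites 5.1.1 expressly when it wants that count. A mean per attack is most naturally divided by the attacks whose durations were summed, and the pain score in SAP 5.2.1 does exactly that by requiring the same period. The rule on attacks with stop before start points the same way: it keeps them in the attack count and the pain score and does not mention the duration divisor. This part of the objection stands, so the 7/k factors belong to one possible reading and not the more natural one.

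It can also be said that step 1 is loose wording for the informative days among the last seven. The blinded-review sentence in SAP 5.2.3 and the protocol support that intention, and if the programs follow it there is no mismatch of days. But step 1 states a different rule in plain terms, and nothing in the SAP overrides it.

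Finally, on the log scale a multiplicative error becomes an additive shift, which largely cancels from the treatment difference when completeness is similar in both arms. That is correct. What remains is added noise, and values that do not match the defined week.

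**Conclusion.** The point holds as a conflict between a stated derivation rule and the endpoint's own definition. For any subject with at least one uninformative day in the calendar week, and earlier informative days to draw on, the step 3 product combines different days under either reading of step 2, and a Visit 4 value can contain days from before week 4. On the more natural reading the size depends on how the added days differ from the week itself: none on average if attack duration is stable, and a factor of 1.29 in the assumed example with two older days of 40-minute attacks. The 7/k factors apply only if step 2 uses the 5.1.1 count, and then only at a constant attack rate and duration.

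A reader might go further and conclude that the treatment comparison is biased. The documents do not support this: they give neither the share of subjects with k below 7 nor any sign that completeness differs by arm, so no bias at trial level can be calculated. The reach is limited. Duration is tested last of the three key secondary endpoints, after pain and the Raynaud's Condition Score, and the primary endpoint does not use this derivation.

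**What to change.** Amend SAP 5.2.3 before unblinding.

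- Step 1: sum the durations of confirmed attacks on the informative days within the seven calendar days before the visit, that is, the same days as in 5.1.1.
- Step 2: divide by the number of those same attacks that have a non-missing duration, so that attacks with stop before start do not enter the divisor.
- Step 3: leave unchanged. The 5.1.1 count already scales for missing days, and attacks without a usable duration then receive the mean duration.

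If no day in the calendar week is informative, the rule yields no value and the missing-data provision of SAP 4.1.2 applies.

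The cost is a change of SAP wording and, if the programs followed step 1 literally, a small programming change. No new data are needed, and days before the calendar week are not required because the scaling in 5.1.1 replaces them. The change does not settle a week with no attacks, where step 2 has no divisor and the log is undefined; that needs its own rule.
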